**Summary of Analyses for Endpoints Related to Hypoglycemia**

Endpoint	Analysis Period	Statistical Method
Rate of severe hypoglycemic events (per patient per year / 100 years)	0-12, 0-26, 12-26 weeks	Exposure adjusted rate per year / 100 years (calculated by total number of events divided by total exposure for individual patients) will be provided and the empirical method (see Appendix 1 for details) will be used for treatment comparison.

Endpoint	Analysis Period	Statistical Method
Incidence of severe hypoglycemic events	0-12, 0-26, 12-26 weeks	Proportion of patients with severe hypoglycemia will be reported. The treatment comparison will be based on a logistic regression model with treatment as an independent variable.

a All documented hypoglycemia and the subcategories based on the thresholds of blood glucose  $\leq 70$  mg/dL and blood glucose  $< 54$  mg/dL will be analyzed, except for postmeal hypoglycemia for which only the threshold of  $\leq 70$  mg/dL will be applied.

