6.2. Exclusion Criteria

Patients will be excluded from study enrollment if they meet any of the following criteria at screening:

Medical Conditions

- [14] Have any other condition (including known drug or alcohol abuse, psychiatric disorder including eating disorder) that precludes the patient from following and completing the protocol
- [15] Have been diagnosed, at any time, with T1D or Latent Autoimmune Diabetes in Adults
- [16] Have hypoglycemia unawareness as judged by the investigator
- [17] Have had any episode of severe hypoglycemia (defined as requiring assistance due to neurologically disabling hypoglycemia) within the 6 months prior to screening
- [18] Have had 1 or more episodes of diabetic ketoacidosis or hyperglycemic hyperosmolar state within the 6 months prior to screening
- [19] Have a known diagnosis of secondary diabetes (for example, diabetes caused by hemochromatosis, acromegaly, chronic pancreatitis, or pancreatectomy)
- [20] Excessive insulin resistance defined as having received a total daily dose of insulin >2.0 U/kg at the time of screening
- [21] Have a history of or are being evaluated for bariatric surgery including Roux-en-Y gastric bypass surgery, gastric banding, and/or gastric sleeve
- [22] Have clinically significant cardiovascular disease, within the last 6 months prior to screening, defined as stroke, decompensated heart failure New York Heart Association class III or IV ([Appendix 6](#)), myocardial infarction, unstable angina pectoris or coronary arterial bypass graft
- [23] Renal:
 - a) History of renal transplantation
 - b) Currently receiving renal dialysis
 - c) Serum creatinine >2.0 mg/dL ($177 \mu\text{mol/L}$) at screening
- [24] Hepatic: Have obvious clinical signs or symptoms of liver disease (for example, acute or chronic hepatitis or cirrhosis), or elevated liver enzyme measurements as indicated below at screening:
 - a) Total bilirubin level (TBL) $\geq 2X$ the upper limit of normal (ULN [with the exception of Gilbert's syndrome]) as defined by the central laboratory,
Or
 - b) Alanine aminotransferase (ALT) $\geq 3X$ ULN as defined by the central laboratory,
Or

- c) Aspartate aminotransferase (AST) $\geq 3X$ ULN as defined by the central laboratory

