### 5.2. Determination of Sample Size

Patients will be randomized in a 2:1 ratio to LY900014 and insulin lispro, both administered 0 to 2 minutes before meals. Assuming a non-inferiority margin (NIM) of 0.4%, no true difference between treatment arms, and an SD of 1.1%, 480 completers (320 in the LY900014 group and 160 in the insulin lispro group) will provide 96% power to show noninferiority between LY900014 and insulin lispro using the upper limit of a 2-sided 95% confidence interval (CI; LY900014 – insulin lispro). Assuming a 15% dropout rate for 26 weeks, approximately 564 patients will need to be randomized.

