  - Other postbaseline data (for example, vital signs, safety laboratory tests, and questionnaires) will be considered as on IP if the measurement was performed at or prior to the cutoff date defined as 14 days after the last IP dose date
- For data collected as running records with an exact date stamp such as adverse events (AEs) and diary entries where the dates of the measures were not tied with the date of an office visit, postbaseline data with dates  $\leq$  (last study drug dose date +1) will be considered as data on IP.

Table 6.2 describes the rules for determining the patient population, baseline and postbaseline observations for the different analysis periods.

For continuous measures, summary statistics will include sample size, mean, SD, median, minimum, and maximum for both the actual and the change from baseline measurements. Least-squares (LS) means and standard errors derived from the analysis models will also be displayed. Treatment comparisons will be displayed showing the treatment difference LS means and the 95% CIs for the treatment differences, along with the p-values for the treatment comparisons.

For categorical measures, summary statistics will include sample size, frequency, and percentages. Fisher's exact test will be used for treatment comparisons.

For laboratory values, Systeme International (SI) units will be presented. Both % and mmol/mol will be presented for HbA1c and mmol/L will be presented for glucose measurements.

All baseline measures will be analyzed using an analysis of variance (ANOVA) model that has treatment as the model term.

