A listing of patients with at least 1 severe hypoglycemia reported (as SAE) after randomization will be provided. Summary of severe hypoglycemia treatment and outcome from the patient diary will be provided.

A list of MedDRA PTs will be used for the narrow search of potential severe hypoglycemia in spontaneously reported AEs. The events identified through the search strategy that are also reported as SAEs will be summarized and compared between treatments. Fisher's exact test will be used to assess the treatment difference in the proportion of patients with potential severe hypoglycemia.

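### Severe-hypoglycemia incidence is compared by treatment-only logistic regression with no rule for an arm with zero events, so the odds ratio and its CI may be unusable

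*SAP*

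**What the plan says.** In SAP Table 6.5 the row for incidence of severe hypoglycemia covers "0-12, 0-26, 12-26 weeks". The proportions are to be reported, and then: "The treatment comparison will be based on a logistic regression model with treatment as an independent variable". No exact, penalised or zero-event alternative is given for this row.

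Four other places bear on it.

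- The row just above it, for the severe event rate, uses the empirical method of SAP Appendix 1 instead of the negative binomial model used for the commoner categories. The rate is the listed secondary endpoint (SAP Table 4.1; Protocol Section 4). Incidence of severe events is not listed.
- SAP 6.1 sets the general rule for categorical measures: Fisher's "exact test will be used for treatment comparisons".
- SAP 6.12.4.1 plans a MedDRA term search for potential severe hypoglycemia among spontaneously reported adverse events. For those also reported as SAEs, Fisher's "exact test will be used to assess the treatment difference in the proportion of patients with potential severe hypoglycemia".
- Protocol 6.2 excludes patients who "Have had any episode of severe hypoglycemia (defined as requiring assistance due to neurologically disabling hypoglycemia) within the 6 months prior to screening", and also those with hypoglycemia unawareness.

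The SAP revision history records that the baseline-rate covariate was removed from all hypoglycemia models. Treatment is therefore the only term left in this logistic model.

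**The concern.** With one binary covariate, logistic regression reproduces the two observed proportions. If one of them is zero, the likelihood keeps rising as the log odds ratio moves towards infinity. Software stops at an arbitrary large value with a huge standard error, and the Wald interval and p-value then reflect the stopping rule more than the data.

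Eligibility removes patients at higher risk of severe events, and 2:1 allocation makes the lispro arm the smaller one. An empty arm is therefore a real possibility if incidence is low. Three windows are analysed, and the two shorter ones contain fewer events. Severe hypoglycemia is a central safety outcome for an insulin. If a fallback has to be chosen after unblinding, the choice is post hoc.

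**Working it through.** **Arm sizes.** SAP 5.2: "Patients will be randomized in a 2:1 ratio to LY900014 and insulin lispro, both administered 0 to 2 minutes before meals"; "Assuming a 15% dropout rate for 26 weeks, approximately 564 patients will need to be randomized". The basis is "Assuming a non-inferiority margin (NIM) of 0.4%, no true difference between treatment arms, and an SD of 1.1" (per cent), with 320 + 160 completers.

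- SE = 1.1 × √(1/160 + 1/320) = 0.1065. Then 0.4/0.1065 − 1.96 = 1.80, so power is 0.964, against 96% stated.
- 480/0.85 = 564.7, against 564 stated.
- 564/3 = 188 on lispro and 376 on LY900014.

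The plan's figures are reproduced.

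**How often an arm is empty.** Assume the same 26-week incidence p in both arms, all randomized patients dosed, and no dropout. Let a = (1−p)^188 and b = (1−p)^376. Then P(exactly one arm empty) = a(1−b) + b(1−a).

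| p | a (lispro empty) | b (LY900014 empty) | exactly one empty, 0-26 weeks |
|---|---|---|---|
| 0.25% | 0.625 | 0.390 | 0.53 |
| 0.5% | 0.390 | 0.152 | 0.42 |
| 1% | 0.151 | 0.023 | 0.17 |
| 2% | 0.022 | 0.001 | 0.02 |

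For the shorter windows, scale incidence to 1−(1−p)^(12/26) and 1−(1−p)^(14/26) and use the same formula.

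| p | 0-12 weeks | 12-26 weeks |
|---|---|---|
| 0.25% | 0.41 | 0.44 |
| 0.5% | 0.52 | 0.53 |
| 1% | 0.45 | 0.40 |
| 2% | 0.19 | 0.14 |

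At 1% and 2% the shorter windows are clearly worse than 26 weeks. At 0.25% they are not, because both arms are then more often empty together. Treating the two short windows as independent, the chance that exactly one arm is empty in at least one of the three windows is about 67% at 0.25%, 78% at 0.5%, 67% at 1% and 31% at 2%.

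**What the model returns.** For 3/376 against 0/188:

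- Stopped after 8 iterations: log OR 4.74, SE 5.3, Wald p = 0.372.
- Stopped after 25 iterations: log OR 21.7, SE about 26,000, Wald p = 0.999.
- Likelihood-ratio p = 0.118; Fisher p = 0.554.
- Firth, which here means adding 0.5 to each cell: OR = (3.5/373.5)/(0.5/188.5) = 3.5, a finite value.

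For 0/376 against 4/188, Wald p is about 0.999 and Fisher p = 0.012. For 0/376 against 3/188, Fisher p = 0.037.

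**How often the conclusion would change.** With an empty lispro arm, Fisher's two-sided p for 1 to 5 LY900014 patients with an event is 1.00, 0.555, 0.554, 0.307 and 0.175. It is 0.057 at 8 and first falls below 0.05 at 9 (0.033). With an empty LY900014 arm, 3 lispro patients suffice. Writing B(x; n, p) for the binomial probability of x events in n patients, P(one arm empty and Fisher p < 0.05) is the sum of B(x; 188, p) × (1−p)^376 over x ≥ 3, plus the sum of B(x; 376, p) × (1−p)^188 over x ≥ 9. It is about 0.5% at p = 0.25%, 1.1% at 0.5%, 0.9% at 1% and 0.8% at 2%.

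**The case against.** **Three stronger readings do not hold.**

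- *An empty lispro arm is likely.* The documents give no event rate. Over 26 weeks the lispro arm is more likely than not to be empty only if incidence is below 1 − 0.5^(1/188), about 0.37%. At 1% the chance is about 15%, and at 2% about 2%.
- *The analysis would often hide a difference that an exact test shows.* At 0.5% incidence, 376 × 0.005, or about 2, LY900014 patients with an event are expected. With an empty lispro arm Fisher's test also finds nothing at such counts. Under equal incidence the few discordant results, about 1% or less, would themselves be chance findings. No true-difference scenario was calculated.
- *The SAP prescribes a Wald test.* It names only the model. A likelihood-ratio test of that model stays finite: p = 0.003 for 0 against 4 and 0.010 for 0 against 3. That the Wald output would be reported is an inference from common software practice.

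**Cover elsewhere.** Every severe episode is an SAE (SAP 6.12.4.1), and Fisher's test is planned for a closely related set of SAEs. Protocol 10.3.4 also compares the proportions of patients with each type of event by Fisher's test. Raw proportions and a listing of patients with severe events will be produced, so a split such as 0 against 4 would be visible. Incidence is outside the multiplicity scheme, and the listed endpoint is analysed by another method.

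Most of this stands, and it limits the weight of the point. It does not close the gap. The term-search set is defined separately, with no 0-12 or 12-26 week split stated. The specific entry in Table 6.5 takes precedence over the general Fisher rule. Nothing says which result governs if the two disagree on nearly the same patients, and none of these analyses is stated to give an interval for the treatment effect.

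**Conclusion.** The point holds as a gap in a supportive safety row. If one arm has no severe events, the planned odds ratio has no finite estimate, and its usual interval and p-value are uninformative. How often this happens depends on an incidence that the documents do not state. Under equal incidence, no dropout and full dosing, it is a real possibility at a 26-week incidence of about 1% or less and uncommon over 26 weeks at 2%, though the two shorter windows remain exposed there (19% and 14%).

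The cost is mainly the loss of a usable effect estimate and interval. A changed p-value conclusion is rare under these assumptions. Neither the primary analysis, nor any multiplicity-controlled test, nor the listed rate endpoint is affected. The text of SAP Appendix 1 was not available for this check, so how the empirical method handles zero events was not assessed.

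**What to change.** In the severe-hypoglycemia incidence row of Table 6.5, for all three windows, replace the logistic regression with Fisher's exact test plus an exact or score confidence interval for the risk difference. Alternatively, keep a regression but specify Firth penalisation with profile-likelihood intervals. Either choice should be fixed before unblinding.

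The cost is one line of SAP text. Fisher's test is slightly conservative. No covariate adjustment is given up, because the planned model has none, and the choice matches the SAP's own method for categorical measures.

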#### 6.12.4.2. Systemic Hypersensitivity Reaction

The number and proportion of patients experiencing treatment-emergent potential systemic hypersensitivity reactions will be summarized and compared by treatment group using Fisher's exact test. The following MedDRA SMQ will be used to identify potential systemic hypersensitivity reactions from all TEAEs:

- Anaphylactic reaction (SMQ). Besides using the narrow and broad terms designated within the SMQ, the following search algorithm will also be implemented as another approach to determine if a patient had an anaphylactic reaction: if a patient (had at least 1 event in Category A) or (had at least 1 event that is in category B and also had at least 1 event that is in category C) or (had at least 1 event that is in category D and [also had at least 1 event in category B or at least 1 event in category C])
- Angioedema (SMQ)
- Hypersensitivity (SMQ)

Specifically, need to perform the following: (1) any narrow or algorithmic term from any 1 of the 3 SMQs indicated above (that is, combined search across narrow and algorithmic portions of all 3 SMQs); (2) any narrow scope term within each SMQ, separately (that is, narrow SMQ search); (3) any term within each SMQ, separately (that is, broad SMQ search); (4) narrow scope term search within each SMQ, report the PT nested within each SMQ.

A similar summary will be provided for the TEAE related to study drug judged by investigator.

Note that an individual patient may contribute multiple events. Also, a single event may satisfy multiple SMQs, in which case the event contributes to every applicable SMQ.

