**Table 6.1. Patient Populations**

Population	Description
Entered	All patients who give informed consent.
Enrolled	All patients who receive at least 1 dose of open-label insulin lispro in the 8-week lead-in period.
Randomized	All patients who are randomly assigned to study treatment at Visit 8. Treatment group will be defined on the basis of the treatment the patients are assigned.
Safety	All randomized patients who receive at least 1 dose of the randomly assigned investigational product (IP). Treatment group will be defined on the basis of the treatment the patients are assigned.
Completer	Patients included in the randomized population who have completed Week 26 of study treatment without permanent discontinuation of IP. Treatment group will be defined on the basis of the treatment the patients are assigned.
Per Protocol	Patients included in the randomized population who have completed Week 26 of study treatment without permanent discontinuation of IP and without significant protocol deviations through Week 26 that would significantly impact the primary objective. Treatment group will be defined on the basis of the treatment the patients actually receive.

Unless otherwise stated, the efficacy analyses will be conducted on the Randomized Population, and the safety analyses will be conducted on the Safety Population.

The primary analysis is for the treatment period through Week 26.

Unless otherwise noted, all tests of treatment effects will be conducted at a 2-sided alpha level of 0.05, and CIs will be calculated at 95%, 2-sided. All tests of interactions between treatment groups and other factors will be conducted at a 2-sided alpha level of 0.10.

The definitions of baseline and post-baseline for the efficacy and safety analyses depend on which analysis period is being used. The following analysis periods will be used:

- Lead-in Period – Visits 2 to 8
- 26-Week Treatment Period – from randomization to Week 26 prior to discontinuation of investigational product (IP)
- 
- 26-Week Treatment Period and Safety Follow-Up Visit – from randomization to Visit 801 (including all data regardless of IP use)

The data on IP is defined based on the following rules:

- For data only measured at an office visit
  - Mixed-meal tolerance test (MMTT) postbaseline data will be classified as on IP if the MMTT performance date is prior to or on the last IP dose date

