The number and percentage of patients with common TEAEs (defined as  $\geq 5\%$  before rounding for LY900014-treated patients) will be summarized by treatment group using MedDRA PT (without regard to SOC). Events will be ordered by decreasing frequency. Treatment will be compared by Fisher's exact test.

The number and percentage of patients who experienced an SAE including deaths and SAEs temporally associated or preceding deaths will be summarized by treatment group using MedDRA PT regardless of SOC. Events will be ordered by decreasing frequency. A listing of all SAEs will also be provided.

The number and percentage of patients who discontinued from study due to an AE will be summarized by treatment group using MedDRA (without regard to SOC) using all data regardless of IP use. The number and percentage of patients who discontinued IP due to an AE will be also summarized by treatment group using MedDRA PT (without regard to SOC) using data prior to permanent discontinuation of IP. Events will be ordered by decreasing frequency. A listing of all AEs as reason for study or IP discontinuation will also be provided.

The number and percentage of patients who experienced other notable TEAEs (potential systemic hypersensitivity reaction, injection site reaction, and hepatic disorder) will be summarized by treatment group using all TEAEs regardless of IP use. For events that are gender-specific (as defined by MedDRA), the denominator and computation of the percentage will include only patients from the given gender.

Table 6.4 summarizes the planned analyses and the requirement of analysis data for different analysis periods. A 'Yes' in the IP USE column indicates that only data collected prior to permanent discontinuation of IP will be included.

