**Table 6.4. Treatment-Emergent Adverse Event Analysis Periods**

Analysis Period	Analysis Population	Analysis	IP USE	Treatment
Lead-in Period	All enrolled patients	AE overview; TEAE by PT; SAE, discontinuation due to AE	N/A	Open-label insulin lispro
Treatment Period (0-26 Weeks)	All patients in safety population	AE overview; TEAE by SOC and by PT; common TEAE; TEAEs by maximum severity; SAE; IP discontinuation due to AE	Yes	LY900014, insulin lispro
Week 0 – Visit 801	All patients in safety population	AE overview; TEAE by SOC; common TEAE; SAE; other notable AEs; study discontinuation due to AE	All data regardless of IP use	LY900014, insulin lispro

Abbreviations: AE = adverse event; IP = investigational product; N/A = not applicable/available; PT = Preferred Term; SAE = serious adverse event; SOC = system organ class; TEAE = treatment-emergent adverse event.

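### The anaphylaxis algorithm in SAP 6.12.4.2 sets no time link between paired events, so unrelated events up to about 30 weeks apart count as a potential anaphylactic reaction

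*SAP*

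**What the plan says.** SAP 6.12.4.2 names three SMQs (Anaphylactic reaction, Angioedema, Hypersensitivity) that "will be used to identify potential systemic hypersensitivity reactions from all TEAEs". For the first it adds an algorithm, described as "another approach to determine if a patient had an anaphylactic reaction". Besides a category A event alone, a patient qualifies in two ways:

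- B with C: "had at least 1 event that is in category B and also had at least 1 event that is in category C".
- D with B or C: "had at least 1 event that is in category D and [also had at least 1 event in category B or at least 1 event"; the clause closes by naming C as the alternative to B.

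The section then lists four outputs. Search (1) takes "any narrow or algorithmic term from any 1 of the 3 SMQs indicated above". Searches (2) to (4) are narrow or broad term searches within each SMQ. The number of patients with potential reactions is compared between arms by Fisher's exact test, and a similar summary covers TEAEs that the investigator judged related to study drug.

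On the period, SAP 6.12.2 says that the notable TEAEs, which include systemic hypersensitivity, "will be summarized by treatment group using all TEAEs regardless of IP use". Table 6.4 places them in its Week 0 to Visit 801 row: "AE overview; TEAE by SOC; common TEAE; SAE; other notable AEs; study discontinuation due to AE". SAP 6.1 defines that period as running "from randomization to Visit 801 (including all data regardless of IP use").

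**The concern.** The algorithm infers one clinical reaction from separately recorded events. That inference makes sense only if the events belong to the same episode, and the rule tests only whether each category ever occurred. A category B event in Week 2 and a category C event in Week 20 satisfy it.

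Systemic hypersensitivity is one of the named notable AEs for a formulation that adds treprostinil and citrate to insulin lispro (protocol 3.2). Anaphylaxis counts are usually read case by case, so one or two chance hits can change how the table reads. If chance hits occur in both arms, they also dilute any real difference. SAP 6.12.7.1 analyses hypersensitivity reaction by antibody status too. It does not say which definition it uses, so the same hits could carry over there.

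**Working it through.** **Inputs from the documents**
- Follow-up: 26-week treatment period plus 4-week safety follow-up (SAP 5.1), 26 + 4 = 30 weeks = 210 days. This matches Visit 801 at week 30 in the protocol's Schedule of Activities (Section 2).
- Planned randomized: 564 at 2:1 (SAP 5.2), so 376 on LY900014 and 188 on insulin lispro.
- Incidence of category B, C and D events: not given. Categories A to D are not defined in either document. All incidences below are assumptions.

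**1. Search for a time link.** SAP 6.12.4.2 contains none, and no other section of either document supplies one for this algorithm. The SAP does deal with timing elsewhere. Section 6.12.4.1 merges hypoglycemia records no more than 30 minutes apart, and 6.12.4.4.3 reviews how close ALT or AST elevations are to bilirubin elevations. AE records have exact dates (SAP 6.1), so a time link can be programmed.

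**2. How far apart chance pairs fall.** For two independent onsets, uniform over 210 days, P(gap > d) = (1 − d/210)².
- d = 30: (180/210)² = 73%
- d = 60: (150/210)² = 51%
- d = 90: (120/210)² = 33%
- Within 7 days: 1 − (203/210)² = 6.6%
- Same or adjacent calendar day: about 3/210 = 1.4% (in continuous time, within 1 day: 1 − (209/210)² = 0.95%)

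A 7-day window would thus drop about 93% of chance pairs, and a same-or-next-day window about 99%. The rule as written keeps all of them.

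**3. Expected chance hits among 564.** With at most one event per category and independence, B with C alone gives 564 × pB × pC. Adding the D branch, the rule is met when at least two of B, C and D occur: P = pB·pC + pB·pD + pC·pD − 2·pB·pC·pD. For 10/8/3% this is 0.0080 + 0.0030 + 0.0024 − 0.00048 = 0.01292, and 564 × 0.01292 = 7.29. The window columns multiply the no-window count by 0.066 or 0.014.

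| Assumed B / C / D | No window | Within 7 days | Same or next day |
|---|---|---|---|
| 3% / 2% / D omitted | 0.34 | 0.02 | 0.005 |
| 10% / 6% / D omitted | 3.4 | 0.22 | 0.05 |
| 2% / 2% / 1% | 0.45 | 0.03 | 0.006 |
| 5% / 5% / 2% | 2.5 | 0.16 | 0.04 |
| 10% / 8% / 3% | 7.3 | 0.48 | 0.10 |

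**4. Split between arms.** With no treatment effect, hits divide 2:1 on average; 7.3 splits into 4.9 and 2.4. If exactly two chance hits occur, both fall on LY900014 with probability (2/3)² = 44%.

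**The case against.** The strongest reply is that this is a sensitive screen and is labelled as one. The section's output is *potential* reactions. The algorithm sits beside narrow and broad searches and enters only search (1). A parallel summary is restricted to events that the investigator judged related, SAEs are listed (6.12.2), and SAEs and AE discontinuations get narratives (6.12.8). Over-counting in a safety screen is a defensible choice. In addition, the categories come from a standard SMQ whose instructions are not in the documents and might address timing.

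Much of this stands. A reader might infer that the plan reports chance pairs as confirmed anaphylaxis; the label and the parallel searches do not support that. A reader might also infer a bias against LY900014. Nothing shows one: treatment is double-blind, both arms have the same planned follow-up, and the comparison is of proportions, so chance pairs are expected at similar rates. A 2-versus-0 split is likely under 2:1 allocation for that very reason, and Fisher's test would not flag it.

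The reply does not remove the gap. The SAP writes the algorithm out and gives it the purpose of deciding whether a patient had an anaphylactic reaction. It places the hits in a count that is formally compared, and it provides no timing review. The relatedness summary removes some unrelated pairs but does not test whether two events formed one episode. Narratives do not cover non-serious events that did not lead to discontinuation. The screen's sensitivity can be kept by retaining the unwindowed count as its own line.

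**Conclusion.** The point holds as a gap in a stated rule. Followed as written, SAP 6.12.4.2 counts category B, C and D events weeks or months apart as a potential anaphylactic reaction and adds them to search (1).

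The size is unknown. The range of roughly 0.3 to 7 patients of 564 follows from assumed incidences, independence and uniform timing. Its low end uses B with C only and its high end includes D. A reader might take this as a forecast of false cases, but the documents give no incidences to support one, and the true number could be near zero.

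The consequence is noise and dilution in one safety summary. It does not affect the primary HbA1c comparison or any multiplicity-adjusted objective. This is an inexpensive improvement worth making, and no specific window length can be derived from the documents.

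**What to change.** Amend SAP 6.12.4.2 before unblinding:

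- Require the events that form an algorithmic case through B with C, or D with B or C, to have onset dates within a short pre-specified window. The same or next day is one example; the sponsor should choose and justify the length.
- Treat partial onset dates as meeting the window.
- Use the windowed result in search (1).
- Keep the unwindowed count as a separate sensitivity or screening line.

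The cost is a few sentences and a date condition in the program, using dates already collected. The downside is that a true case with misrecorded onset dates could drop out of the windowed count; the screening line would still show it. The window should be fixed before treatment codes are known, because one chosen after seeing the cases by arm would look post hoc.
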